Decision aids- based on evidence and theory- can help with difficult decisions. Decision aids are tools that facilitate decision-making and have been developed and used for medical issues from acne treatment to weight control, but rarely (to date) for decisions about "life issues." A unifying, recommended model for decision aid development is the Ottawa Decision Support Framework (Figure 1). which draws upon concepts from psychology, decision conflict, social support, and self-efficacy. The framework posits that decisional needs (e.g., knowledge, conflict/uncertainty, and values) affect decision quality, with the highest quality decision being one that is both informed and reflective of the individual's values. Decision guality, in turn, affects patient actions and, ultimately, impacts both health outcomes and patient's feelings about the decision. The overall assertion is that the highest quality decision will have the best outcome for the patient. Therefore, decision aids can enhance decision quality by addressing unmet decisional needs; specifically, decision aids facilitate complicated decisions by (a) identifying the decision to be made. (b) describing risks and benefits of various options, (c) assisting the patient in clarifying personal values, and (d) activating the patient for decision-making. In a Cochrane review of 115 randomized trials (with 34,444 participants total), decision aids improved multiple decision outcomes, including knowledge, satisfaction, decisional conflict and regret, and communication.

Older drivers need a tool to help their decision-making. Various guides and self-assessment tools exist to help older drivers and their families think about driving, but what was missing was a tool to walk a driver through the process of deciding whether or not to stop driving. Decision aids have been developed for financial, long-term care, and end-of-life issues, and a small pilot (n=12) found a paper-based driving decision aid (DDA) acceptable and useful, although their tool is specific to individuals with dementia in Australia (which has different laws and systems of alternative transportation). Healthwise, a nonprofit organization that provides decision support tools and other services to enhance patient-centered decision making,

Table 1. Driving Decision Aid content						
Section	Description					

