## **Outcome Measures and Analysis:**

AUTO Study Protocol: Version Date: 12/22/21 PI: [name], MPH COMIRB No: 19-0059 Key measures in this trial (Table 3, additional details below) are tied directly to our theoretical framework (Figure 1) and assess DDA effects (Aim 1) and potentially differential subgroup effects (Aim 2).

Immediate outcomes: Our primary outcome will be the DDA's effect on decision quality, a fundamental element of the Ottawa Decision Support Framework as a precursor to behavior change (Figure 1). A high quality decision is defined as an informed patient making a decision consistent with their values.

-Decision Conflict: The Decisional Conflict Scale (DCS) measures internal conflict or ambivalence about the decision, with higher internal conflict (or ambivalence) indicating the decision is less in-line with personal values. The DCS is closely linked to overall decision quality and is a recommended primary outcome measure. The DCS estimates decisional conflict through personal perceptions of issues such as uncertainty in choosing options, modifiable factors contributing to uncertainty, and effective decision-making (e.g., expressing satisfaction with the choice). The DCS is a 16-item scale (with Likert scale response options) that has high reliability and test-retest correlation (Cronbach's alpha coefficients > 0.78). In prior work, the DCS has been shown to discriminate between known groups who make or delay decisions (effect size 0.4-0.8), with lower scores indicating low decision conflict (and greater likelihood of implementing a decision). Scores <25 (out of 100 total) are associated with implementing decisions.

-Values Concordance: We will use the "Values Clarity" subscale of the DCS to examine specifically how much participants feel their decisions are in line with their values. Three DCS items are summed and multiplied by 8.33; scores range from 0 (extremely clear) to 100 (extremely unclear about personal values).

-Knowledge: Questions will assess concepts about driving presented in the DDA and control group website.

-Self-Efficacy: We will measure decision self-efficacy (one's self-confidence or belief in one's ability to make decisions) using the Decision Self-Efficacy Scale, as decision aids can increase self-efficacy. Transformed scores range from 0 (extremely low) to 100 (extremely high self-efficacy).

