Aim 1a. Test the DDA's effect on immediate decision quality (measured by the Decisional Conflict Scale). Hypothesis 1a: More DDA participants will have high-quality (DCS<25) scores, compared to control, immediately after the intervention. Our primary outcome measure will be the proportion of participants with DCS score <25. We will perform multiple logistic regression to test the DDA's effect on decision quality. We are also interested in jointly modeling the proportion of family members with DCS score <25, so a bivariate logistic regression model will be used for analysis to allow assessment of marginal effects of the intervention on patients and family members, as well as their concordance/discordance in decision quality. In the small pilot trial of Australian drivers with dementia, mean DCS score scores decreased from 22.5 to 7.5 (out of 100) after the DA; should we find that DCS score distributions do not allow dichotomization based on the cut-point of 25, we will instead compare means between the groups. Missing data for the primary measure should be minimal, given that this will be obtained at enrollment. Additional analyses will include examining components of decision quality to identify changes in

AUTO Study Protocol: Version Date: 12/22/21 PI: [name], MPH COMIRB No: 19-0059 measures like knowledge, values-concordance, or self-efficacy, as they may shed light on the mechanisms underlying decision-making about driving.

Family member data: In addition to the analysis under 1a, we will examine the degree of concordance (or discordance) within driver-family dyads on various measures, including current versus desired level of family involvement in driving retirement process (part of the driving questionnaire). To evaluate agreement we will look at the kappa coefficients at baseline and at follow-up points, as well as apply this class of repeated-measure concordance correlation coefficients. For longitudinal data, we will examine changes across the other time points (6, 12, 18, 24 months) using GEE after adjusting covariates.

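### DCS<25 alone shows low decisional conflict, not a high-quality decision as the protocol defines it, and Aim 1a names no adjustment for pre-exposure DCS

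*Combined protocol and SAP*

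**What the plan says.** **Definition.** Under Outcome Measures and Analysis (Immediate outcomes): "A high quality decision is defined as an informed patient making a decision consistent with their values". Background and Significance gives the same two conditions, "with the highest quality decision being one that is both informed and reflective of the individual's values".

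**Endpoint.** Aim 1a: "Our primary outcome measure will be the proportion of participants with DCS score <25". Hypothesis 1a labels that result: "More DDA participants will have high-quality (DCS<25) scores, compared to control, immediately after the intervention". The Aim 2 analyses reuse the same dichotomy.

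**Instrument.** "The DCS estimates decisional conflict through personal perceptions of issues such as uncertainty in choosing options". Of the cut-point the protocol says: "Scores <25 (out of 100 total) are associated with implementing decisions". It also states that the DCS is closely linked to decision quality, that higher conflict points to a decision less in line with values, and that the scale is a recommended primary measure.

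**Knowledge and values.** Table 3 lists a knowledge questionnaire, given to drivers before and after exposure, as a descriptive secondary outcome with no threshold. The values concordance outcome is the three-item Values Clarity subscale of the 16-item DCS, on which "scores range from 0 (extremely clear) to 100 (extremely unclear about personal values".

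**Baseline.** Table 3 has drivers complete the DCS before and after exposure, but gives it only the role of primary outcome. Aim 1a specifies multiple logistic regression and does not name pre-exposure DCS as a covariate. The only pre-aid level quoted is from the Australian pilot: "mean DCS score scores decreased from 22.5 to 7.5 (out of 100) after the DA". If the distribution does not allow a cut at 25, means will be compared instead.

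**The concern.** The definition needs two things: the person is informed, and the choice fits their values. The criterion tests neither directly. A driver who feels certain but has learned nothing from either website meets DCS<25 and fails the protocol's own definition. The knowledge data that would separate these cases are collected but play no part in the rule. The values outcome measures how clear people feel about their values, and its items already sit inside the primary score.

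What is at stake is the wording of the main conclusion. The overarching hypothesis and Aim 1a both speak of high-quality decisions, and a reader of the results would take that phrase in the sense the protocol gives it.

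The second matter is efficiency. A driver below 25 before exposure who stays there counts as a success in either arm and adds nothing to the arm difference. If such drivers are common, the effect is diluted, and a model without the pre-exposure score leaves out information the trial has collected. If they are more common in one cognitive group than the other, the unadjusted Aim 2a interaction becomes harder to read.

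**Working it through.** **1. Definition against criterion.**

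| Element of the definition | In DCS<25? | Where it is measured |
|---|---|---|
| Informed (tested knowledge) | No | Knowledge questionnaire, secondary, no threshold |
| Consistent with values | Partly, as perceived clarity | Values Clarity, 3 of the 16 DCS items (3/16 = 19%) |
| Felt certainty | Yes | DCS |

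The gap is clear for the informed half and partial for the values half.

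**2. The plan's own sample size.** Inputs from Sample Size: 150 per arm, 10% loss, so 150 × 0.9 = 135 per arm; difference at least 20 points; 0.05 level; power 90%. Arm proportions are not in the text, so I assume 40% against 60%, the 20-point gap giving the lowest power among those tried.

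Power = Φ{[|p1−p0|√n − 1.96√(2p̄(1−p̄))] / √(p0(1−p0)+p1(1−p1))}, where p̄ is the mean of p0 and p1.

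[0.2 × 11.62 − 1.96 × 0.707] / 0.693 = (2.324 − 1.386)/0.693 = 1.35, so power = 0.91. The stated 90% reproduces. The sample size is sound for its own endpoint.

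**3. Share below 25 before exposure.** Mean 22.5 is from the pilot. The SD is not given and is assumed, with a normal shape. Share = Φ((25 − 22.5)/SD).

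- SD 10: Φ(0.25) = 0.60
- SD 15: Φ(0.167) = 0.57
- SD 20: Φ(0.125) = 0.55

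At SD 20 the normal curve puts Φ(−22.5/20) = 13% of scores below zero, so the shape is only rough.

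**4. Dilution.** Let a share b start and stay below 25 in both arms, and let the rest respond 40% (control) against 60% (DDA). Then p0 = b + 0.4(1−b), p1 = b + 0.6(1−b), and the difference is 0.2(1−b).

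| b (assumed) | Control | DDA | Difference | Power at 135 per arm |
|---|---|---|---|---|
| 0 | 40% | 60% | 20 points | 0.91 |
| 0.20 | 52% | 68% | 16 points | 0.77 |
| 0.40 | 64% | 76% | 12 points | 0.58 |
| 0.55 | 73% | 82% | 9 points | 0.42 |
| 0.60 | 76% | 84% | 8 points | 0.38 |

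At b = 0.55, a 20-point overall difference needs 0.20/0.45 = 44 points among the rest.

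**5. Aim 2a.** Take the same 40% against 60% among drivers who start at 25 or above.

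- No drivers already low: OR = (0.6/0.4)/(0.4/0.6) = 2.25.
- 55% already low: OR = (0.82/0.18)/(0.73/0.27) = 1.69.

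The odds ratios differ although the aid works identically among drivers able to cross the cut. This shows the mechanism only: the documents give no baseline DCS by cognitive status.

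**6. Power of an informed-and-low-conflict responder.** Assume independence, DCS<25 in 40% against 60%, and adequate knowledge in share k of both arms.

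- k = 0.5: 20% vs 30%, power 0.48
- k = 0.7: 28% vs 42%, power 0.68
- k = 0.8: 32% vs 48%, power 0.77

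If the DDA also raises adequate knowledge from 50% to 70%, the comparison is 20% vs 42%, with power 0.98.

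**The case against.** The strongest reply is that the proxy is declared. Aim 1a says that decision quality is measured by the DCS, and the protocol links the scale to values and calls it a recommended primary measure. Knowledge, values clarity and self-efficacy are secondary outcomes to be examined as components of decision quality. The secondary analyses for Aim 2 include a split by cognitive insight. The fallback to means shows that the authors saw the cut-point problem. All of this stands, and it is good reason to keep DCS<25 as primary. It does not make the criterion equal to the definition: separate descriptive analyses cannot show how many low-conflict drivers were also informed. The fallback has no stated trigger and does not bring in knowledge.

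A reader might infer more than the documents support:

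- *The arm comparison is biased.* Randomization balances baseline-low drivers in expectation. The consequence is dilution.
- *Over half of these drivers will start below 25.* That figure rests on a pilot of 12 drivers with dementia using a different, paper-based aid, plus an assumed SD. This trial excludes 5-minute MoCA scores under 21.
- *Only drivers starting at 25 or above matter.* The endpoint is the post score. A driver below 25 can also rise above it after either website and so contribute to the difference. Restricting to baseline DCS≥25 would, at the shares in step 3, keep only about 54 to 61 of 135 per arm.
- *Values Clarity is passed off as independent.* The protocol openly calls it a DCS subscale. The defect is the name values concordance.

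**Conclusion.** The point holds as a mismatch between the endpoint and the claim. As written, a positive Aim 1a or Aim 2 result would license a statement about low decisional conflict and not one about high-quality decisions in the protocol's sense. This follows from the text alone and needs no assumption.

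The baseline part is conditional. Leaving pre-exposure DCS out of the named Aim 1a model is a plain omission, but its cost depends on how many drivers start below 25, which the documents do not give for this population. Across assumed shares of 0 to 60%, a 20-point effect among the rest becomes 20 down to 8 points overall, with power 0.91 down to 0.38 at 135 per arm.

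It may be tempting to conclude that Hypothesis 2a would be confirmed as an artefact of the cut-point. The documents do not support that. Baseline differences by cognitive status could complicate the unadjusted interaction, but nothing shows that they exist or in which direction they run.

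**What to change.** 1. Keep DCS<25 as the primary outcome, and state the Aim 1a and Aim 2 conclusions as low decisional conflict.
2. Pre-specify a secondary responder: DCS<25 and post-exposure knowledge at or above a pass mark fixed before unblinding. Compare it by arm in Aim 1a and use it as a supportive analysis in Aim 2a.
3. Include pre-exposure DCS as a covariate in the Aim 1a model and in a supportive Aim 2 interaction model. Do this in place of any restriction to drivers with baseline DCS≥25.
4. Call the secondary outcome values clarity, and note that its three items are part of the 16-item DCS.

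**Cost.** The change is to plan wording and a few added analyses, with no new visits or data. The headline claim becomes narrower, and a knowledge pass mark must be chosen, since the documents give none. The added responder may be underpowered (step 6), so it should be supportive only. Covariate adjustment yields a conditional odds ratio, so the arm proportions should be reported beside it, because the sample size is stated as a difference in proportions.

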## AUTO Study Protocol: Version Date: 12/22/21 PI: [name], MPH COMIRB No: 19-0059 **Table 3. Key study measures**. Shown in relation to measurement point (pre- or post- DDA or website

Participant, and analytic plan. • = about self,  $\circ$  = as surrogate about older driver

		[name]/friends			Analytic Plan				
Domaiı	n and Key Measures	En	roll	F/u	Enr	oll	F/u			
		Pref	Post		Pre	Post			Hypoth.	Scoring
Immediate outcome										
Decision Conflict	Decisional Conflict Scale (DCS)	•	•	•	٠	•	•	1° Outcome	1a, 2a, 2b, 2c	Score <25
Knowledge	Knowledge questionnaire	•	•	•		•	•	2° Outcome	1a	Descriptive (cat.)
Values concordance	DCS Values Clarity subscale	٠	٠	•	٠	٠	٠	2° Outcome	1a	Descriptive (cat.)
Self-efficacy	Decision Self-Efficacy scale	•	•	•		•	•	2° Outcome	1a	Descriptive (contin.)
Longitudinal outcome										
Depression	PROMIS depression	٠		٠				2°	1b	T-score >50
								Covariate	1c	Descriptive (contin.)
Decision regret	Ottawa Decision Regret Scale			•			•	2° Outcome	1b	Descriptive (contin.)
Life space	Life-Space Assessment	٠		•			0	2° Outcome	1b	Descriptive (contin.)
Driving behaviors	Amount; reduction or cessation	•		•			0	2° Outcome	1c	Descriptive (cat.)
Subgroups										
Cognitive	5 minute MoCA			٠			•	Eligibility		Score ≥21
screening								Covariate	•	
Cognitive function	BTACT, OTMT	•						Stratify	2a	Normal vs. impaired
Insight	Beck Cognitive Insight Scale	٠		٠				Stratify	2a	R-C index ≥3
Decisional capacity	SPACED	•		•				Stratify	2b	# correct answers
Attitudes about	ARMT	٠		٠				Stratify	2c	Mean score ≥3.57
anning								Covariate	1c	_0.07

	Drivers	Family/fri	Analytic Plan				
Domaii	n and Key Measures	Enroll F	/u Enroll	F/u			
		PrePost	Pre Post			Hypoth.	Scoring
Other covariates							
Demographics	E.g., age, gender, race/ethnicity, marital/home status, education, income, urban/rural	•	• •	•	Covariate	all	Descriptive (cat.)
Physical health	Medical history, Activities of Daily Living, PROMIS global health	•	•	•	Covariate	all	Descriptive (cat.)
Mental health	PROMIS Emotional Support, Social Isolation; Perceived Stress Scale	•	•		Covariate	1b, 1c	Descriptive (cat.)
Personality	TIPI	•			Covariate	1c, 2c	Descriptive. (cat.)
Driving behaviors	Crashes, self-driving technologies	•	•	0	Covariate	1c	Descriptive (cat.)
Driving resources	Alternative transportation, support	•	••	• 0	Covariate	1c	Descriptive (cat.)
Driving education	Use of websites, courses, or other material driving or cessation	•	• •	•	Covariate	1c	Descriptive (cat.)

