Analysis for Aim 1: Analyses will be performed according to the principle of intention-to-treat. including all randomized drivers. Unless otherwise specified, hypothesis tests will be two-sided with alpha=.05, with 95% confidence intervals or p values reported. All canalyses will be performed using SAS/STAT® software. First, descriptive statistics will be computed for baseline patient characteristics, initially testing for differences between control and intervention groups (including for key covariates, Table 3.3). We will assess site effects by comparing demographic variables across the sites, using ANOVA for continuous measures and chi-square tests of proportions for categorical measures. If no statistically significant differences exist among sites. we will ignore site and formally test the differences in proportions or means as described below. If there are significant differences among sites, then (assuming enough events) we will use separate bivariate logistic regression models for each aim described below, with a fixed effect for site and with treatment arm as the main predictor. For longitudinal analyses, we will conduct logistic regression with unstructured correlation of generalized estimating equations (GEE) to account for the repeated observations for each participant. Statistical significance will be evaluated at one-sided p<.05 level. Analyses of the DDA's longitudinal effects may be vulnerable to bias, as control arm participants may be exposed to intervention arm messages through exposure to available materials or courses related to driving safety or cessation (e.g., websites, physician counseling, AARP courses). We will assess exposure to other sources of information through structured questions. To mitigate the impact of this potential bias, we will adjust measurements of contamination as applicable. In all analyses, validation of distributional and parameterization assumptions will be checked and data transformations (e.g. logtransformations) or alternative methods will be implemented as appropriate.

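### The pre-intervention Decisional Conflict Scale score is collected but not named as a covariate in any Aim 1a analysis; naming it is an optional efficiency gain

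*Combined protocol and SAP*

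**What the plan says.** All references are to the combined protocol and SAP.

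- **Table 3, Key study measures.** The DCS row is marked pre, post and follow-up, for drivers and for family or friends. Its only analytic role is primary outcome, for hypotheses 1a, 2a, 2b and 2c. Other measures carry two roles: PROMIS depression is an outcome for 1b and a covariate for 1c, and the ARMT is a stratifier for 2c and a covariate for 1c. Demographics, physical health and life events are covariates for all hypotheses; the family questionnaire is a covariate for 1a.
- **Baseline Measurements & Intervention.** The introductory questionnaire comes before the decision aid or control website, so the pre score precedes exposure.
- **Aim 1a.** The primary outcome is the proportion with DCS below 25. The plan is "We will perform multiple logistic regression to test" the decision aid's effect, without a covariate list. For dyads, "a bivariate logistic regression model will be used for analysis to allow assessment of marginal effects of the intervention on patients and family members"; again no covariates are listed. The fallback reads "should we find that DCS score distributions do not allow dichotomization based on the cut-point of 25, we will instead compare means", with no baseline term. On missingness: "Missing data for the primary measure should be minimal, given that this will be obtained at enrollment".
- **Analysis for Aim 1.** If demographics do not differ among sites, "we will ignore site and formally test the differences in proportions or means as described below". If they do, the model is fitted "with a fixed effect for site and with treatment arm as the main predictor". Neither branch mentions baseline DCS.

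**The concern.** The outcome is a scale score re-measured in the same session, so its own starting value is an obvious candidate covariate, and the trial already pays to collect it from both members of each dyad. When such a covariate is prognostic, including it raises the power of the treatment test and narrows the interval for a standardized risk difference. With no list in the text, two analysts could fit different primary models, and the choice could be made after the data are seen.

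What is at stake is precision, chiefly if the true difference is below the 20 points used for planning. The Sample Size section says that no effect estimates exist for this aid in older drivers, so a smaller difference cannot be ruled out.

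**Working it through.** **Inputs from the documents.** 300 drivers, 150 per arm; 90% power; significance level 0.05; 10% loss; difference of 20 to 40 points (Sample Size). Tests two-sided unless otherwise specified (Analysis for Aim 1).

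**Inputs assumed.** The text gives neither arm proportions nor a pre/post correlation. I take 40% versus 60% (a 20-point difference centred on 50%, where it is hardest to detect), 40% versus 55% (a smaller effect), and r = 0.3, 0.5, 0.7 on a latent normal scale.

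**Step 1: reproduce the plan's sample size.** Per arm, with p̄ the mean of the two proportions,

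n = [1.960·√(2p̄(1−p̄)) + 1.282·√(p₁(1−p₁)+p₂(1−p₂))]² / (p₁−p₂)².

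For 40% versus 60%: [1.960×0.7071 + 1.282×0.6928]² / 0.04 = 2.274² / 0.04 ≈ 129.3, so 130 per arm, 260 in total, and 260/0.9 = 289. For 30% versus 50% the total after loss is 276, or 298 with continuity correction. The stated 300 is consistent with a 20-point difference.

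**Step 2: power without the baseline score.** At 150×0.9 = 135 per arm, 40% versus 60%: z = (0.20×√135 − 1.960×0.7071)/0.6928 = (2.324 − 1.386)/0.6928 = 1.354, power 0.912. For 40% versus 55%: z = (0.15×√135 − 1.960×0.7062)/0.6982 = (1.743 − 1.384)/0.6982 = 0.514, power 0.696. The stated 90% is met at 20 points.

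**Step 3: power with the baseline score.** A latent normal post score is cut to give the stated proportions, and a pre score is correlated r with it. The test is a Wald test for arm in logistic regression, without and with the continuous pre score; 10,000 trials per setting.

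| Per arm | Proportions | Arm only | r = 0.3 | r = 0.5 | r = 0.7 |
|---|---|---|---|---|---|
| 135 | 40% vs 60% | 0.905-0.907 | 0.929 | 0.949 | 0.980 |
| 135 | 40% vs 55% | 0.678-0.684 | 0.721 | 0.774 | 0.848 |
| 150 | 40% vs 60% | 0.934-0.935 | 0.949 | 0.964 | 0.990 |
| 150 | 40% vs 55% | 0.741-0.742 | 0.762 | 0.810 | 0.886 |

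A separate simulation (2,000 trials per setting, 135 per arm) gave 0.886-0.908 unadjusted and 0.927 / 0.945 / 0.977 adjusted for 40% versus 60%; and 0.681-0.690 unadjusted and 0.733 / 0.764 / 0.857 adjusted for 40% versus 55%. With no effect (50% in both arms) the adjusted test rejected in 4.6-5.2% of trials in the larger run and 3.9-5.1% in the smaller.

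**Step 4: the same gain as sample size.** In the 2,000-trial run at 40% versus 60%, the variance of the standardized risk difference fell to 0.949 / 0.815 / 0.700 of the unadjusted value. Dividing 270 analysed drivers by these ratios gives about 285 / 331 / 385 effective drivers.

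**Step 5: the means fallback.** Analysis of covariance multiplies the variance by 1 − r² = 0.91 / 0.75 / 0.51.

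**The case against.** The best defence is that the plan does not leave baseline DCS out; it leaves it unstated. Aim 1a says *multiple* logistic regression, whereas Aims 2a and 2b say *simple* for arm-only models, and calling arm the main predictor does not close the model to other terms. Table 3 already supplies several covariates. This stands: a reader might infer that the plan gives up the baseline score, and the text does not support that. Nor does the word settle the matter the other way, since Analysis for Aim 2 uses *multiple* for models of arm, subgroup and interaction that it calls unadjusted.

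It also stands that the arm-only comparator is not quite the model in Aim 1a, that r is assumed, that at r = 0.3 the gain is only two to four points, and that 40% versus 55% lies below the planned range. The contrast with Aim 1b is weak too: it lists examples of baseline adjustment but does not name baseline outcome values.

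Three further inferences are tempting and unsupported:

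- *The pilot mean of 22.5, already below 25, shows that the starting score is prognostic.* A mean carries no information on pre/post correlation, and the pilot had 12 participants, using a paper tool, among Australian drivers with dementia.
- *The fallback to means inflates type I error.* Under the stated distribution-based condition, simulated error with a pooled trigger was 4.7-5.5%. Inflation would need selection of the smaller p-value, which nothing in the plan suggests.
- *The fallback should be dropped in favour of DCS below 25 alone.* It protects against a ceiling. With about 89% versus 96% below 25 (assumed latent means 12.5 and 7.5, SD 10, 150 per arm, no baseline adjustment), power is about 60% for proportions and 99% for means.

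**Conclusion.** The point holds as an optional efficiency improvement. No part of the document names the pre-intervention DCS as a covariate in the Aim 1a logistic model, the driver-family model or the means fallback. There is no bias. A reader might infer an underpowered trial; Step 2 shows otherwise at the planned 20 points.

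At 135 per arm the possible gain is roughly 2 to 7 percentage points of power for 40% versus 60% and 4 to 17 for 40% versus 55%, with type I error near 5%. These figures rest on assumed correlations of 0.3 to 0.7, assumed arm proportions, a latent normal score and an arm-only comparator. The gain over a model already containing the Table 3 covariates was not computed, so the figures are illustrative rather than a measure of what this plan loses. They concern drivers; Potential Challenges and Strategies says that the power calculations are based on driver participation.

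**What to change.** 1. Name the driver's continuous pre-intervention DCS as a covariate in the Aim 1a logistic model, whether or not sites differ.
2. In the bivariate model, enter each member's own pre-intervention DCS with its own coefficient.
3. Keep the planned fallback to means, and use the same baseline term there (analysis of covariance).
4. Report a standardized (marginal) risk difference with 95% CI beside the conditional odds ratio. This also serves the plan's stated interest in marginal effects.
5. State a simple rule for a missing baseline value, such as the pooled pre-intervention mean.

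**Cost.** No new data: the score is already scheduled for both groups. The work is SAP text and a standardization step in the program. The downside is that the adjusted odds ratio is conditional on baseline DCS and not directly comparable with an unadjusted one. Adjustment does not shrink the standard error of the log odds ratio; the benefit appears as power and as precision of the standardized risk difference, which is why item 4 belongs with item 1.

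### The primary endpoint may change from DCS below 25 to mean DCS once score distributions are seen, with no numeric trigger and no requirement to decide on pooled, arm-masked data

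*Combined protocol and SAP*

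**What the plan says.** Under Outcome Measures and Analysis, Aim 1a states: "Our primary outcome measure will be the proportion of participants with DCS score <25". It expects to test this by logistic regression on scores taken straight after the decision aid or control website. It then cites a small pilot in which "mean DCS score scores decreased from 22.5 to 7.5 (out of 100) after the DA", and continues that if "DCS score distributions do not allow dichotomization based on the cut-point of 25, we will instead compare means between the groups".

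Other parts of the plan that bear on this:

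- **Table 3** scores the primary outcome only by the cut at 25.
- **Sample Size** gives 150 drivers per arm, a 20 to 40 point difference in the share below 25, 90% power, a 0.05 level and 10% loss. It gives no target difference or SD for mean DCS.
- **Aim 2a** dichotomizes DCS at 25 and has no fallback. Aim 2b also uses the dichotomized outcome.
- **Analysis for Aim 1** sets the default: "hypothesis tests will be two-sided with alpha=.05, with 95% confidence intervals or p values reported". A later sentence, placed after the longitudinal GEE model, reads "Statistical significance will be evaluated at one-sided p<.05 level".
- **Randomization** says that staff who deliver the intervention are unblinded and that other study staff are blinded to arm. It does not mention the statistician or the choice of endpoint.
- **Data Management** lets the principal investigator, biostatistician and analyst see all sites' data, and is silent on whether arm is masked.

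**The concern.** The fallback is named in advance, but the condition for using it is not defined. A logistic model can be fitted whenever neither arm is at 0% or 100%, so the condition must refer to something less extreme, and the plan does not say what. Nor does it say whether pre- or post-intervention scores are judged, whether arms are pooled, who decides, or when. Post-intervention DCS is collected at enrollment, so the outcome data build up from the first participant.

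Two things are at stake. First, the wording permits an arm-aware choice between two primary tests, and a reader of the results could not verify that the switch was warranted. Second, if the switch happens, the trial's main test has no stated power, and Aims 1 and 2 would rest on different endpoints.

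**Working it through.** **1. The plan's own figure.** Inputs from Sample Size: 150 per arm, 10% loss (150 × 0.90 = 135 evaluable), two-sided 0.05, 20-point difference. The least favourable pair is 40% versus 60%.

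- Power: z = (0.20 × √135 − 1.960 × √(2 × 0.5 × 0.5)) / √(0.4 × 0.6 + 0.6 × 0.4) = (2.324 − 1.386) / 0.693 = 1.354, so power is 91.2%.
- Sample size at 90% power: (1.386 + 1.2816 × 0.693)² / 0.20² gives 130 per arm. Then 130 / 0.90 gives 145, or 290 in total. With a continuity correction the total is 312.

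The stated 300 lies between these, so the 90% is reproduced for the proportion.

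**2. Power of the fallback.** With 135 per arm and 90% power, the detectable mean difference is (1.960 + 1.2816) × √(2/135) = 0.39 SD. The documents give no SD. Assuming 15, this is 5.9 points; assuming 20, it is 7.9 points. Neither figure appears in the plan.

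**3. Worst-case error if the better test is chosen.** 20,000 null trials were simulated per scenario, with 150 per arm. Scores were drawn from a beta distribution on 0 to 100, rounded to the steps of the 16-item scale. The tests were a pooled z-test on DCS below 25 and a large-sample test of means, both two-sided at 0.05. All means and SDs are assumptions. The Monte Carlo standard error near 5% is √(0.05 × 0.95 / 20,000) = 0.15 points.

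| Mean / SD | Share <25 | Correlation of tests | Proportion alone | Means alone | Either test significant |
|---|---|---|---|---|---|
| 7.5 / 8 | 95.1% | 0.67 | 4.70% | 5.25% | 8.49% |
| 7.5 / 12 | 90.6% | 0.83 | 5.15% | 5.19% | 7.75% |
| 10 / 12 | 87.8% | 0.81 | 4.92% | 5.20% | 7.81% |
| 15 / 15 | 77.8% | 0.84 | 4.98% | 5.25% | 7.77% |
| 20 / 15 | 67.1% | 0.83 | 4.88% | 5.26% | 7.77% |
| 22.5 / 15 | 60.8% | 0.82 | 5.13% | 5.00% | 7.77% |
| 22.5 / 20 | 62.3% | 0.84 | 4.91% | 5.02% | 7.51% |
| 30 / 18 | 43.4% | 0.79 | 5.34% | 4.93% | 8.14% |

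Each test alone holds its level. Choosing the better one gives 7.5% to 8.5%. If one-sided 0.05 were used, the range is 7.2% to 8.2%.

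**4. The same data with a fixed pooled trigger.** The rule was to switch to means when the share below 25, pooled over arms, exceeds 80%, 85%, 90% or 95%. Type I error was 4.8% to 5.3% across all scenarios. It held where the trigger fired only some of the time: with mean 7.5, SD 12 and a 90% threshold, the switch occurred in 59.9% of trials and the error was 5.0%.

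**5. When the dichotomy loses its value.** With equal arms and a pooled share P below 25, the largest possible difference is 2 × (1 − P). At P = 90% this is 20 points, the smallest difference the trial was sized for. Above 90% that difference cannot occur.

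**The case against.** The strongest defence is that the rule turns on the shape of the distribution and not on test results, and that the alternative is stated beforehand. Step 4 supports this: a switch driven by the pooled distribution costs essentially nothing in type I error. A reader might infer that the rule in itself raises the error to about 8%. The documents do not support that, because the inflation arises only if arm-level results are seen and the favourable test is picked.

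Other stronger readings also fail:

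- **That a switch is likely because the pilot means lie under 25.** A mean under the cut does not prevent dichotomization. At an assumed mean of 22.5, about 61% to 62% of scores fall below 25, an ordinary split. The Background describes the pilot as 12 people using a paper aid specific to dementia in Australia. It shows that the authors foresaw a switch, no more.
- **That there is no blinding.** Randomization blinds other study staff in general terms. What is missing is an express requirement that covers this decision.
- **That one cannot tell what the 90% power refers to.** Sample Size ties it to DCS below 25.
- **That the sentence allowing "data transformations (e.g. logtransformations) or alternative methods will be implemented as appropriate" lets the team replace the endpoint.** It concerns the checking of model assumptions.

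What remains is that a named alternative with an undefined condition does not fix the choice in advance, and nothing in the plan rules out an arm-aware decision.

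**Conclusion.** The point holds as an undefined, unmasked switching rule on the trial's main test. The worst-case type I error is about 7.5% to 8.5% against a nominal 5%. This rests on assumed DCS means of 7.5 to 30, SDs of 8 to 20, a beta shape and 150 per arm. With a fixed pooled trigger the excess disappears. Separately, and without any assumption about conduct, the fallback has no stated power, no specified model and no matching rule in Aim 2. The design is adequately powered for DCS below 25. This deserves correction before any analysis by arm, because it governs the primary test and costs little to repair.

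**What to change.** Choose one of two.

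1. **Single primary.** Keep DCS below 25, delete the switch, and report mean DCS adjusted for baseline DCS as a named secondary in every case. The downside is lower power if nearly all scores fall below 25.
2. **Defined fallback.** Switch only if the post-intervention share below 25, pooled over arms and masked to arm, exceeds a stated number (for example 90%, for the reason in step 5). Record and date the decision before any analysis by arm. Specify the means model as ANCOVA on baseline DCS, state its detectable difference (about 0.39 SD at 135 per arm and 90% power, before any gain from baseline adjustment), and carry the same endpoint into Aim 2.

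The trigger should use post-intervention scores. Baseline scores could miss the floor that the authors feared, since the pilot mean fell to 7.5 only after the aid.

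Under either option, state that the primary test is two-sided, so that the one-sided sentence cannot be read as applying to it. The cost is protocol and SAP wording only. Table 3 already has DCS collected before and after the intervention, so no new data or participants are needed.
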